#### Data Collection and Analysis Dataset:

Data will be collected on the baseline and follow-up CRFs. Data will be summarized on the Attempted Subjects analysis set.

#### Analysis Method:

NYHA class will be summarized using descriptive statistics for categorical variable described in **Section 7.2** by visit. For subjects with paired data, change from baseline will be summarized as both a categorical and a continuous variable using appropriate statistics described in **Section 7.2**.

- Procedural times

#### Hypothesis/Decision Criteria:

No specific hypotheses or pass/fail criteria have been set. The analysis will be descriptive and no statistical hypothesis tests are planned.

#### Endpoint Definition/Parameters to Be Estimated:

This endpoint is defined using variables on the procedure CRF.

- Anesthesia time is defined as anesthesia (procedure) stop time minus anesthesia (procedure) start time.
- Intubation time is defined as extubation time minus anesthesia (procedure) start time.
- Total procedure time (skin-to-skin) is defined as thoracic incision closure time minus thoracic incision start time.
- Deployment time is defined as final TMVR deployment time minus TMVR delivery catheter insertion time.
- Apical access duration is defined as apical access closure time minus apical incision time.
- Rapid pacing duration is defined as the "Pacing duration during deployment".

## Data Collection and Analysis Dataset:

Data will be collected on the procedure CRF. Data will be summarized on the Attempted Subjects analysis set.

## Analysis Method:

Each procedure time will be summarized using descriptive statistics for continuous variable described in **Section 7.2**.

- Re-hospitalizations for heart failure through 5 years

## Hypothesis/Decision Criteria:

No specific hypotheses or pass/fail criteria have been set. The analysis will be descriptive and no statistical hypothesis tests are planned.

## Endpoint Definition/Parameters to Be Estimated:

This endpoint is defined using the CEC adjudication for re-hospitalization for heart failure on the AE CRF.

## Data Collection and Analysis Dataset:

Data will be collected on the AE CRF. Data will be summarized on the Attempted Subjects analysis set.

## Analysis Method:

This endpoint will be summarized using descriptive statistics for time to event data described in **Section 7.2**. Kaplan-Meier event rates at 30 days, 6 months, 12 months, and every 6 months through 5 years.

- MVARC defined technical success

## Hypothesis/Decision Criteria:

No specific hypotheses or pass/fail criteria have been set. The analysis will be descriptive and no statistical hypothesis tests are planned.

## Endpoint Definition/Parameters to Be Estimated:

This endpoint is defined using variables on the AE and procedure CRFs.

Technical success is measured at exit from the catheterization laboratory and all of the following must be present:

- Absence of procedural mortality (free from death on day 0, which is day of procedure, AE CRF); and
- Successful access, delivery, and retrieval of the delivery system (same definition as secondary endpoint, procedure CRF); and
- Successful deployment and correct position of the first intended device (TMVR implant is "Yes", no additional devices opened or used, TMVR device malfunction is "No", and TMVR device failure is "No", procedure CRF); and
- Freedom from emergency surgery or reintervention related to the device or access procedure (Conversion to open MV replacement is "No" and Other repair surgery is "No", procedure CRF).

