## **Appendix B: Participant Information and Consent Form**

## **Appendix C: Instructions for Use**

## Appendix D: Endpoint Definitions

Analysis of study results will include the following additional MVARC defined exploratory endpoints:

**Technical Success** (measures at exit from catheterization laboratory)

All of the following must be present:

- I. Absence of procedural mortality; and
- II. Successful access, delivery, and retrieval of the device delivery system; and
- III. Successful deployment and correct positioning of the first intended device; and
- IV. Freedom from emergency surgery or reintervention related to the device or access procedure

**Device Success** (measured at 30 days and at all later post-procedural intervals):

All of the following must be present:

- I. Absence of procedural mortality or stroke; and
- II. Proper placement and positioning of the device; and
- III. Freedom from unplanned surgical or interventional procedures related to the device or access procedure; and
- IV. Continued intended safety and performance of the device, including:
  - a. No evidence of structural or functional failure
  - b. No specific device-related technical failure issues and complications
  - c. Reduction of MR to either optimal or acceptable levels without significant mitral stenosis (i.e., post-procedure EROA is 1.5 cm^2 with a transmural gradient <5 mm Hg), and with no greater than mild (1+) paravalvular MR (and without associated hemolysis)

**Procedural Success** (measured at 30 days)

All of the following must be present:

- I. Device success (either optimal or acceptable), and
- II. Absence of major device or procedure related serious adverse event, including:
  - a. Death
  - b. Stroke
  - c. Life-threatening bleeding (MVARC scale)
  - d. Major vascular complications
  - e. Major cardiac structural complications
  - f. Stage 2 or 3 acute kidney injury (includes new dialysis)
  - g. Myocardial infarction or coronary ischemia requiring PCI or CABG
  - h. Severe hypotension, heart failure, or respiratory failure requiring intravenous pressors or invasive or mechanical heart failure treatments such as ultrafiltration or hemodynamic assist devices, including intra-aortic balloon pumps or left ventricular or biventricular assist devices, or prolonged intubation for 48 h
  - i. Any valve-related dysfunction, migration, thrombosis, or other complication requiring surgery or repeat intervention

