## 4. Study Objectives

The primary objective of the study is to evaluate the safety of the Intrepid™ TMVR System:

- The primary endpoint is the assessment of the nature, severity and frequency of complications associated with the delivery and/or implantation of the device.

The secondary objective of the study is to evaluate the performance of the Intrepid™ TMVR System:

- The secondary endpoints include assessment of:
  - The degree of improvement of MR grade and symptoms, and the durability of TMVR function.
  - The ability to accurately deliver and place the implant within the native anatomy.
  - The fit of the implant within the native anatomy, including fixation, sealing and compatibility with native structures (e.g., other components of the mitral valve apparatus, the conduction system, and the left ventricular outflow tract (LVOT)/aortic valve).

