#### Endpoint Definition/Parameters to Be Estimated:

This endpoint is defined using variables on the AE, procedure and core lab echo CRFs.

Device success is measured at discharge, 30 days and at all later post-procedure intervals. All of the following must be present:

- Absence of procedural mortality or stroke (free from death and stroke within 30 days of procedure, AE CRF); and
- Proper placement and positioning of the device (TMVR implanted is "Yes", procedure CRF); and
- Freedom from unplanned surgical or interventional procedures related to the device or access procedure (Conversion to open MV replacement is "No" and Other repair surgery is "No", procedure CRF); and
- Continued intended safety and performance of the device, including
  - o No evidence of structural or functional failure (free from AEs for device malfunction for structural or functional failures, and free from explant and MV reinterventions, AE CRF)
    - Delivery failure (i.e., technical failure)
    - Structural failure
    - Functional failure
  - o No specific device-related technical failure issues and complications (core lab echo, AE, procedure CRF)
    - Paravalvular leak (core lab echo, AE CRF)
      - Major/Minor: Having a major paravalvular leak is considered as having a device failure.
    - Coronary vessel compression or obstruction (defined using CEC code, AE CRF)
      - Major/Minor: Having a major coronary vessel compression or obstruction is considered as having a device failure.
      - Symptomatic/Not symptomatic: Having a symptomatic coronary vessel compression or obstruction is considered as having a device failure.

- Requiring treatment/Not requiring treatment: Having a coronary vessel compression or obstruction requiring treatment is considered as having a device failure.
- Transient/Persistent: Having a persistent coronary vessel compression or obstruction is considered as having a device failure.
- Pericardial effusion (defined using CEC code, AE CRF)
  - Major/Minor: Having a major pericardial effusion is considered as having a device failure.
- Conversion to open mitral valve surgery during a transcatheter procedure (Conversion to open MV replacement is "No", procedure CRF)
- Device malpositioning (defined using CEC code, AE CRF)
- Device detachment (defined using CEC code, AE CRF)
  - Partial/Complete: Having a complete device detachment is considered as having a device failure.
- Device fracture (defined using CEC code, AE CRF)

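### Pilot SAP: the technical-success and device-success placement components contain no position variable, so a CEC-coded malposition can pass technical success and be counted as properly placed

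*Combined protocol and SAP*

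**What the plan says.** This point concerns the pilot study, CIP-1403, and its SAP. The transseptal early feasibility plan in the same file is a separate study.

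- **What the CIP requires.** CIP-1403 Appendix D lists for technical success "Successful deployment and correct positioning of the first intended device". For device success it lists, as a separate item, that the device be properly placed and positioned. SAP section 4 names among the secondary aims "The ability to accurately deliver and place the implant within the native anatomy".
- **Technical success (SAP 7.9.3).** The position component reads "Successful deployment and correct position of the first intended device (TMVR implant is 'Yes', no additional devices opened or used", and the same line continues "TMVR device malfunction is 'No', and TMVR device failure is 'No', procedure CRF". That makes four conditions.
- **Device success (SAP 7.9.3).** The placement component reads "Proper placement and positioning of the device (TMVR implanted is 'Yes', procedure CRF". This is one condition.
- **Elsewhere in device success.** Under "No specific device-related technical failure issues and complications (core lab echo, AE, procedure CRF" the SAP lists "Device malpositioning (defined using CEC code, AE CRF", with no grade exempted. For detachment it says "Having a complete device detachment is considered as having a device failure". It does not name partial detachment as a failure.
- **Reporting.** Each composite needs success on every component, and the success rate of each component is also reported on its own. Procedural success and individual subject success both require device success.

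**The concern.** Appendix D treats being deployed and being correctly positioned as separate requirements. The SAP turns the second into the first. A valve can be implanted, with no second device opened and no malfunction or failure recorded, and still sit in the wrong place.

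Two results could then be wrong as reported. Technical success, an outcome a reader would use to judge accurate placement, could count a malpositioned valve as a success. In the device-success table, the placement row would repeat the implant rate. It could also contradict the malpositioning row beside it, with the same subject passing one and failing the other.

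The SAP does not disclose the substitution. Where it drops a consensus criterion from individual subject success (return to the pre-procedural setting), it says so and cites data availability. No such note covers positioning, and SAP 7.12 states that the planned analyses are aligned with CIP-1403.

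**Working it through.** The plan states no figure to reproduce. SAP section 6 treats up to 95 subjects and says the size is not statistically derived. The check is therefore a trace of the scoring rules, followed by an illustration of scale.

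**Step 1. Trace the rules.** Take one isolated event at a time. Assume the valve stays in, no additional device is opened or used, malfunction and failure are both No, and there is no conversion or other repair surgery, no reintervention, no major paravalvular leak, and no other failing item.

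| Event | Technical-success position component | Device-success placement component | Device-success composite |
|---|---|---|---|
| CEC-coded malposition | Pass | Pass | Fail (malpositioning item) |
| Partial detachment | Pass | Pass | Pass |
| Complete detachment | Pass | Pass | Fail (detachment item) |

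For the malposition row, the remaining technical-success components are no death on day 0; successful access, delivery and retrieval; and no conversion or other repair surgery. None of them refers to position, so the technical-success composite also passes. Because the device-success composite fails, procedural and individual subject success fail with it.

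**Step 2. Scale, for illustration only.** The documents give no malposition rate, so the count k is assumed. Suppose all n = 95 subjects are implanted, k are malpositioned, and nothing else fails.

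- Rate as the SAP scores it: 95/95 = 100%.
- Rate with position counted: (95 − k)/95. Each valve is worth 1/95 = 1.05 percentage points.
- Interval: Clopper-Pearson, the exact type the SAP names for these composites. With x successes, the lower limit is the 0.025 quantile of Beta(x, n − x + 1) and the upper limit is the 0.975 quantile of Beta(x + 1, n − x). The upper limit is 1 when x = n.

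| k (assumed) | Successes | Rate | Exact 95% CI |
|---|---|---|---|
| 0 | 95/95 | 100% | 96.2 to 100 |
| 1 | 94/95 | 98.9% | 94.3 to 100.0 |
| 2 | 93/95 | 97.9% | 92.6 to 99.7 |
| 3 | 92/95 | 96.8% | 91.0 to 99.3 |
| 5 | 90/95 | 94.7% | 88.1 to 98.3 |

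These shifts apply to the device-success placement component. They apply to technical success only for malpositions with onset on day 0. For malposition, the change in the device-success composite is zero.

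**The case against.** The strongest reply is that the SAP already catches malposition. Any CEC-coded malpositioning fails device success and hence procedural and individual subject success, so three of the four MVARC composites are already correct for it. This stands, and it limits the point to technical success and the two component rows. A reader might infer that malpositioned or migrated valves pass as successes throughout the analysis. The documents do not support that.

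Three narrower replies also carry weight.

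- **Partial detachment.** One might call its omission from the failures an error. The SAP fails only the more severe grade for paravalvular leak, pericardial effusion, fracture and thrombosis too, and nothing in Appendix D says that partial detachment must fail. A partly detached valve can still fail through a major leak, a functional-failure event, a reintervention or a malposition code. The graded rule is a defensible choice.
- **The secondary delivery endpoint.** One might also fault SAP 7.9.2 because successful delivery there has no position content. The CIP endpoint it implements covers access, delivery and retrieval only, so the SAP matches it.
- **Unseen forms.** The procedure CRF is not in the documents. A site might record a misplaced valve as a malfunction or failure, and technical success would then fail. That is possible, but the SAP does not require it, and neither label means position.

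It is also true that the endpoints are exploratory and are listed only in the US and French CIPs. They carry no pass/fail criterion. Device- or procedure-related events are listed, and case summaries go to the FDA. Malposition would therefore not be hidden from a careful reader. This lowers the consequence but does not correct a rate reported under the name of correct position.

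**Conclusion.** The point holds in a limited form. Neither placement component measures position. A CEC-coded malposition passes the technical-success composite and both placement components when no additional device, malfunction, failure, conversion or repair surgery is recorded. In device success, the placement row can then disagree with the malpositioning row. The device-success, procedural-success and individual-subject-success composites are unaffected by this defect.

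The size depends on how many malpositions occur and how sites fill in the malfunction and failure fields. Neither is in the documents. Under the assumptions above, each malpositioned valve is worth about one percentage point at 95 subjects.

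No hypothesis test, error rate or sample size is involved. This is a scoring rule that can give a wrong result on exploratory, descriptive endpoints. It should be corrected before the final five-year analysis, but it does not put the primary safety result in doubt.

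**What to change.** In SAP 7.9.3:

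1. **Technical success.** Add to the position component: and no CEC-coded device malpositioning with onset on day 0. The endpoint already draws on the AE CRF and already uses a day-0 rule for death, so this fits its structure.
2. **Device success.** Score the placement component as TMVR implanted Yes and no CEC-coded device malpositioning, so that it agrees with the malpositioning item in the same composite.
3. **Partial detachment.** Keep the graded rule, state outright that partial detachment is not scored as a failure, and add a sensitivity row that counts it as one.

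No change is needed to the delivery endpoint in SAP 7.9.2.

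The cost is a few lines of SAP text and code, because device success already uses the CEC code. Technical-success and placement rates may come out slightly lower. The change should be documented as SAP 7.12 requires. If technical success has already been reported at an interim analysis, show both scorings.

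One limit remains: the fix reaches only malpositions that are reported as adverse events and coded by the CEC, which is also the limit of the existing device-success item.

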#### Data Collection and Analysis Dataset:

Data will be collected on the AE and procedure CRFs. Data will be summarized on the Attempted Subjects analysis set.

#### Analysis Method:

The proportion of subjects with technical success will be presented with its associated 95% exact confidence interval. The numerator will include subjects with success in all components of this endpoint. The denominator will include subjects who have success or at least one failure component present.

The proportion of subjects with success for each component of this endpoint will also be presented; the numerator will include subjects with success, and the denominator will include subjects with non-missing data

- MVARC defined device success

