## **7.4 Handling of Missing, Unused, and Spurious Data and Dropouts**

Every effort will be undertaken to minimize missing, unused, and spurious data and dropouts. In time-to-event outcomes, drop-outs will be censored at the time of discontinuation, consistent with the Kaplan-Meier approach.

Unless otherwise specified in each objective, no statistical techniques will be used to impute missing data for continuous or categorical outcomes. If a subject's data are missing for any reason, that subject will not be included in that portion of the analysis. The number of subjects included in each analysis will be reported so that the reader can assess the potential impact of missing data.

In the case of partial dates, if only the month and year are known, the event or assessment will be analyzed as if it occurred on the 15th of that month. If only the year is known, the event or assessment will be analyzed as if it occurred on June 30th of that year. These resolutions of partial dates are subject to the restrictions that events must occur no earlier than the procedure date or after study exit. For more complex imputations of dates, determination will be made on a case-by-case basis based on the most suitable date range.

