## Endpoint Definition/Parameters to Be Estimated:

This endpoint is defined using variables on the procedure CRF.

- Successful access is "Yes" if "TMVR delivery catheter insertion time" is not blank.
- Successful delivery of implant is "Yes" if "Was the TMVR implanted?" is answered "Yes" and "Conversion to open surgical MV replacement" is answered "No".
- Successful retrieval delivery system is "Yes" if "Delivery catheter removal time" is not blank.

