## Endpoint Definition/Parameters to Be Estimated:

This endpoint is defined using variables on the AE, procedure, discharge, baseline, follow-up, and core lab echo CRFs.

Individual subject success is measured at 1 year. All of the following must be present:

- Device success (either optimal or acceptable) (as defined above); and
- No re-hospitalizations or reinterventions for the underlying condition (e.g., MR heart failure) (AE CRF); and
- Improvement from baseline of symptoms (e.g., NYHA improvement  $\geq 1$  functional class) (baseline and follow-up CRFs); and
- Improvement from baseline in functional status (e.g., 6MWT improvement  $\geq 50$  meters) (baseline and follow-up CRFs); and
- Improvement from baseline in QoL (e.g., MLHFQ decline  $\geq 10$  points) (baseline and follow-up CRFs).

The following criterion in the MVARC definition is not included in the definition of individual subject success of this study due to data availability:

- Subject returned to pre-procedural settings

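### Device success and 1-year individual subject success: the composite denominator drops subjects of undetermined status but keeps known failures, so partly missing data shift the reported rate and the SAP does not show by how much

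*Combined protocol and SAP*

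**What the plan says.** The Analysis Method paragraphs for all four MVARC composites in SAP 7.9.3 (technical, device, procedural and individual subject success) use the same pair of rules. For the numerator: "The numerator will include subjects with success in all components of this endpoint". For the denominator: "The denominator will include subjects who have success or at least one failure component present". The rows for single components use a different base: "the denominator will include subjects with non-missing data".

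SAP 7.4 sets the defaults: "Unless otherwise specified in each objective, no statistical techniques will be used to impute missing data for continuous or categorical outcomes", and "If a subject's data are missing for any reason, that subject will not be included in that portion of the analysis". It also promises the number of subjects included in each analysis.

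The sources differ by composite. For device success, reported at discharge, 30 days and every later interval: "This endpoint is defined using variables on the AE, procedure and core lab echo CRFs". For individual subject success at 1 year: "This endpoint is defined using variables on the AE, procedure, discharge, baseline, follow-up, and core lab echo CRFs". All composites are summarised on the Attempted Subjects set with a 95% exact confidence interval. The SAP's Version History records that version 4.0 refined these denominators so that subjects with any failure are included.

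**The concern.** To count as a success, a subject must have every component known. To count as a failure, one known failing component is enough. A subject with a gap in the data is therefore kept or dropped according to the outcome seen elsewhere.

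This matters most for device success after 30 days. Several failures are fixed early and stay known at every later visit: death or stroke within 30 days, valve not implanted, conversion to open surgery. MR grade, orifice area, gradient and paravalvular MR need a core lab echo at each visit. Early failures remain in the denominator, while event-free subjects without an echo leave it. A series of visit rates can then decline because echo completeness declines.

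Individual subject success adds NYHA, 6MWT and MLHFQ, so it has more ways to be partly missing. There is no control arm, and SAP section 5 says results will be read against historical literature. The point estimate and its interval are what readers will compare.

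**Working it through.** The documents give no expected success rate, component failure rate or missingness rate, so there is no figure of the plan's to reproduce. Every rate below is an assumption, except the maximum of 95 subjects (SAP section 6).

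**1. Direction when data are missing completely at random.** A true success is counted with probability P(all components observed). A true failure is counted with probability P(at least one failing component observed), which is never smaller. The rule's expected rate is therefore at or below the truth. It equals the truth if nothing is missing, if there are no failures, or if all components go missing together.

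**2. Size, one component missing.** Let p be true success, m the share with that component missing at random, and q the share failing some other component.

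- Rule: (1−m)p / [(1−m) + mq]
- Undetermined counted as failure: (1−m)p
- Undetermined counted as success: (1−m)p + m(1−q)

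| m | Rule, p=50%, q=40% | Bounds | Rule, p=70%, q=10% | Bounds |
|---|---|---|---|---|
| 5% | 0.475/0.970 = 49.0% | 47.5–50.5% | 0.665/0.955 = 69.6% | 66.5–71.0% |
| 10% | 0.450/0.940 = 47.9% | 45.0–51.0% | 0.630/0.910 = 69.2% | 63.0–72.0% |
| 20% | 0.400/0.880 = 45.5% | 40.0–52.0% | 0.560/0.820 = 68.3% | 56.0–74.0% |
| 30% | 0.350/0.820 = 42.7% | 35.0–53.0% | 0.490/0.730 = 67.1% | 49.0–76.0% |

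**3. Comparability across visits.** Take 95 subjects, 20 early failures and no later failure. With complete echo the rate is 75/95 = 78.9%. If 30 event-free subjects lack an echo at a later visit, it is 45/65 = 69.2%, although no valve has changed. The bounds at that visit are 45/95 = 47.4% and 75/95 = 78.9%.

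**4. Individual subject success.** Assume independent failures: two event-based components 20% each, echo 20%, NYHA 20%, 6MWT 50%, MLHFQ 30%. True success is 0.8⁴ × 0.5 × 0.7 = 14.3%. The four visit measures are missing in 20%.

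- Missing independently: counted successes 0.1434 × 0.8⁴ = 0.0587. Observed failures 1 − 0.64 × 0.84 × 0.84 × 0.60 × 0.76 = 0.7941. Rate 0.0587/0.8528 = 6.9%.
- Missing together: counted successes 0.1434 × 0.8 = 0.1147. Observed failures 0.36 + 0.64 × 0.776 × 0.8 = 0.7573. Rate 0.1147/0.8720 = 13.2%.

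**5. Informative missingness can reverse the sign.**

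- Event failure 10%, echo failure 20%, echo missing in 40% of echo failures and 10% of echo successes. Successes 0.9 × 0.8 × 0.9 = 0.648; failures 0.1 + 0.9 × 0.2 × 0.6 = 0.208. The rule gives 0.648/0.856 = 75.7% against a true 72.0%.
- Event and echo failure 20% each, 10% dying after day 30 with no other failure, echo otherwise 10% missing, and death regarded as failure. Truth is 0.8 × 0.8 × 0.9 = 57.6%. Successes 0.576 × 0.9 = 0.5184; failures 0.2 + 0.8 × 0.2 × 0.9 × 0.9 = 0.3296. The rule gives 0.5184/0.8480 = 61.1%. Device success lists death only within 30 days, so these deaths need not appear as failures.

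**The case against.** The rule is deliberate and has a good reason. SAP 7.1.3 and 7.2 exclude valve-function data after explant, so known failures will often have no later echo. Dropping them as incomplete would inflate success. This stands, and it is why a plain complete-case denominator is not the remedy, although it would be unbiased under completely random missingness.

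Fewer components can go missing than the lists suggest. Most device-success items are freedom from a reported or CEC-coded event, where no report reads as success. This also stands. In practice the gaps are core lab echo and, for the 1-year composite, NYHA, 6MWT and MLHFQ. Technical success uses only AE and procedure forms, and under the SAP's definition of access and retrieval a blank time is simply not a success, so the effect there is probably small.

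The plan partly covers the point: SAP 7.4 reports the number included, 7.1.1 tabulates attrition and visit completion, and component rows show non-missing counts. Much could be found by subtraction. But the SAP does not commit to the undetermined count or to the range of rates it allows, and the component rows rest on different bases.

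The endpoints are exploratory with no pass/fail criterion, and at 95 subjects an exact interval is about 20 points wide (47/95 gives 39% to 60%). That limits the consequence but does not make the rate unbiased.

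A reader might infer that the rule always understates success, whatever the reason for missing data. The documents do not support that. They say nothing about the missingness mechanism, and step 5 of the working shows plausible patterns with the opposite sign.

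**Conclusion.** The concern holds for device success and individual subject success. The same sentence under procedural and technical success matters less. Under partial, completely random missingness the as-written rate is too low. In the assumed one-component cases the shortfall runs from under one point (70% true success, 10% failing elsewhere, at most 10% missing) to 7.3 points (50%, 40% and 30% missing). The 1-year composite could lose about half its value if four visit measures go missing independently in 20% (6.9% against 14.3%), but only about one point if they go missing together.

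The direction is not guaranteed, because it depends on a mechanism and on rates that the documents do not give. What can be said without assumptions is that the reported rate depends on completeness as well as on outcome, and that the SAP does not plan to show the reader how far. No decision rule is affected. This is a cheap improvement to make before the final 5-year analysis.

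**What to change.** Keep the as-written rate. In SAP 7.9.3, for each composite and visit, add:

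- the number of Attempted subjects due at that visit whose status is undetermined, meaning no observed failure and at least one component missing;
- deaths after day 30 as a separate count, with a statement of whether they belong to the set due at the visit;
- the rate on all Attempted subjects due at that visit, with undetermined subjects counted first as failures and then as successes, each with its exact 95% confidence interval.

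The two rates bracket the full-set rate whatever the missingness mechanism. Their intervals are needed because the bounds alone ignore sampling error. The cost is a few extra rows per composite and a wider stated range. No new data are needed.
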